Before any studies investigating the radioprotective effects of locally administered melatonin can be undertaken in humans, it is imperative that the pharmacokinetic properties of melatonin are investigated when administered in this way. No previous studies investigating the pharmacokinetics of vaginal, intravesical, or rectal administration of melatonin have been performed [23]. The few studies investigating transdermal administration of melatonin have been insufficient [24-26]; only one study has been able to estimate a $T_{1/2}$, and only in two volunteers [27], and no studies have investigated transdermal bioavailability [23].

Study design

Objective

The aim of the study is to determine the pharmacokinetic properties of, and possible adverse reactions of, melatonin when administered intravenously, rectally, intravesically, vaginally, and transdermally, in healthy female volunteers.

Design

This study is a crossover study, including five individual study sessions investigating five different routes of administration of melatonin. Four of the study sessions (intravenous, rectal, intravesical, and vaginal) will consist of one study day and one plasma sample the following day. The transdermal application will consist of one study day, followed by plasma samples at 24 and 48 hours following application. Between each study session, the subjects will have a washout period of a minimum of 7 days. The study will include a total of ten healthy female volunteers.

The subjects will participate in study sessions in the following order: intravenous, rectal, intravesical, vaginal, and transdermal administration. The study will be concluded after the

48-hour plasma sample after transdermal administration. Should a participant be menstruating at the time of the vaginal administration study session, the session will be postponed for one week.

Study course

Study session 1: Intravenous administration

The melatonin will be administered intravenously, followed by plasma samples over the following 24 hours. The intravenous melatonin will be dissolved in an ethanol/saline solution (2 ml 99.9 % ethanol/23 ml 0.9 % saline) containing 25 mg of melatonin. The infusion of melatonin will be performed over 10 minutes, the infusion rate being 2.5 mL per minute.

Study session 2: Rectal administration

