Simple reaction time (SRT) test: Subjects will be assessed by an online-based test (<http://getyourwebsitehere.com/jswb/rttest01.html>). Each volunteer will be instructed to press the mouse button as soon as possible, when a stoplight displayed on a computer screen changes from red to green. During the four first study sessions, each volunteer will be tested at baseline (before administration of melatonin), and once every hour for 8 hours after administration of melatonin, as well as 24 hours after administration of melatonin. For the transdermal study session, the test will be performed at every hour on the first day until 16 hours, as well as at 24 and 48 hours.

Other adverse reactions include pre-specified self-reported symptoms of nervousness, confusion, depressed mood, dizziness, headache, garlic breath and burning sensation from application area (yes/no). Volunteers will also be asked to report additional symptoms of adverse reactions, if any (yes/no + description). Results will be noted in the CRF.

When the subjects are included, a set of baseline demographics data will be recorded in the CRF, including date of birth, ethnicity, weight, height, and BMI.

Subjects/population

Inclusion criteria:

- Healthy female
- 20-40 years old
- BMI 18-30

Exclusion criteria:

- Inability to understand Danish, written or spoken.

- Current use of melatonin or other hypnotics/sedatives
- Current pregnancy (a positive urine-HCG; the subjects will be tested prior to each study session)
- Breast feeding
- Current alcohol or drug abuse (defined as over 5 units of alcohol per day, or any usage of illegal drugs)
- Mental illness (defined as being in medical treatment)
- Serious comorbidity (American Society of Anesthesiologists (ASA) physical status 3-4)
- Participation in other clinical trials less than 1 month prior to current study
- Night-shift work within the last 14 days prior to study
- Planned night-shift work within the study period
- Known and diagnosed sleep-disorder (defined as being in current medical treatment)
- Plasma hemoglobin <7.8 mmol/L (measured when screening participants)

Withdrawal and dropout criteria

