The number of patients needed for this study is not based on a power calculation. We have decided that 8 subjects are needed to collect information of how the plasma concentrations develop over time. Because of the risk of dropouts, we have chosen to include a total of 10 subjects.

Data will be presented as either mean (SD) or median (IQR), unless stated otherwise.

Data will be analyzed using IBM SPSS Statistics for Windows version 22.0 (IBM Corp., Armonk, NY, USA) and Graph Pad Prism version 7.0 (Graph Pad Software Inc., La Jolla, CA, USA).

Time to maximal concentrations (t_{\max}) and maximal plasma concentrations (C_{\max}) will be assessed directly at the relevant time points. The pharmacokinetic variables: absorption constant (k_a), absorption half-life ($t_{1/2}$ absorption), elimination rate constant (k_e) and elimination half-life ($t_{1/2}$ elimination) will be estimated by “the method of residuals” [57]. Areas-under-the-curve (AUC) of plasma concentrations will be calculated by applying the trapezoidal rule [58]. $AUC_{0-\infty}$ will be estimated as $AUC_{0-8 \text{ hours}} + (C_{8 \text{ hours}}/k_e)$. Bioavailability (f) will be calculated as follows:

$$f = 100 \times \frac{AUC_{0-\infty} (\text{rectal, intravesical, vaginal or transdermal}) \times D_{iv}}{AUC_{0-\infty} (iv) \times D_{\text{rectal, intravesical, vaginal or transdermal}}}$$
 where D represents the dose

administered.

Data monitoring and management

This study will be conducted in compliance with the protocol, the ICH-GCP guidelines and the applicable regulatory requirements. The standard procedures for quality control and quality assurance are followed in compliance with the ICH-GCP guidelines, and investigator/sponsor allows direct access to data/documents for monitoring, auditing, and inspection from both the Danish Medicines Agency (Lægemiddelstyrelsen) and the Good Clinical Practice (GCP)-unit. The GCP-unit will monitor the study. Data will be stored electronically on a secure server until 10 years

after the end of the study, after which all person-sensitive data are deleted. Blood samples will be destroyed after analysis, at a maximum of one year after sampling. A biobank will be created, solely containing these blood samples. Until analysis, the blood samples are kept in a locked freezer at -80°C (with a temperature-alarm) in a locked room at Gastroenheden D, Herlev Hospital. The blood samples will be analyzed with the RIA-technique at Gaslab, Herlev Hospital.

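### One fixed, unexplained route order aliases route with session number; reaction time is the clearest exposure, and the plan has no practice run or change-from-baseline summary

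*Combined protocol and SAP*

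**What the plan says.** Under Study design, Design: "This study is a crossover study, including five individual study sessions investigating five different routes of administration of melatonin". The same section then fixes the sequence for everyone: "The subjects will participate in study sessions in the following order: intravenous, rectal, intravesical, vaginal, and transdermal administration". No randomised or alternative sequence, no drug-free session and no reason for the order appear anywhere in the document.

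Two timing rules go with it. Between sessions "the subjects will have a washout period of a minimum of 7 days". The other rule is "Should a participant be menstruating at the time of the vaginal administration study session, the session will be postponed for one week"; it moves a date and describes no change of order.

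For reaction time in the first four sessions (Secondary outcomes), "each volunteer will be tested at baseline (before administration of melatonin), and once every hour for 8 hours after administration of melatonin", and again at 24 hours. The transdermal session runs hourly to 16 hours, then 24 and 48 hours. The Karolinska sleepiness score follows the same pattern. No training run is described.

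Statistics plans summaries as mean (SD) or median (IQR). It has no test, no period term and no change-from-baseline rule. The one between-route calculation is bioavailability, a ratio to the intravenous AUC. On size, the section says: "The number of patients needed for this study is not based on a power calculation". Eight completers are judged enough, and two more are enrolled as a margin for losses. Dropouts' data are not analysed (Withdrawal and dropout criteria).

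**The concern.** A crossover lets each subject act as her own control, but separating treatment from time requires that treatments appear in different periods for different subjects. Here they never do. Anything that changes with session number is credited to the route: familiarity with a test, habituation to a rating scale, readiness to report a symptom, or a change of assay batch.

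The aim covers adverse reactions as well as pharmacokinetics for each route, so readers will set the five routes side by side on sleepiness, reaction time and symptoms. The intravenous session, always the first, would be compared with sessions in which the subject has had 10 to 40 more tests. Every bioavailability figure also rests on a denominator from session 1.

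**Working it through.** **Inputs.** Five routes in one order; 10 subjects planned, 8 completers required; the test and sampling schedules (Study design, Secondary outcomes, Statistics). There is no power calculation to reproduce; the only size arithmetic is 8 + 2 = 10.

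**1. Aliasing.** Fit a linear model with subject, period and route, and compare ranks.
- Fixed order, n = 10: subject + period 14; subject + period + route 14. Route df after period: 14 − 14 = 0 of 4.
- Fixed order, n = 8: 12 − 12 = 0 of 4. More subjects do not help.
- If period is replaced by a single slope, linear in prior tests, 14 − 11 = 3 of 4 df are recovered. The route trend that runs along the session order stays inseparable.

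**2. Practice.** Tests per session in sessions 1–4: 1 baseline + 8 hourly + 1 at 24 h = 10. Prior tests at the start of sessions 1 to 5: 0, 10, 20, 30, 40. The transdermal session itself has 1 + 16 + 2 = 19.

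**3. Size for reaction time (illustrative).** A linear drift of d per session shifts the raw difference between the first and fifth sessions by (5 − 1)d = 4d. The documents give no value for d. If d is assumed to be 5–10 ms, 4d is 20–40 ms. This applies to raw scores only. For change from the session's own baseline, an additive shift (k − 1)d in session k is in both terms and cancels.

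**4. Size for bioavailability (illustrative).** If AUC drifts by a factor g per session, f for the session-k route is multiplied by g^(k−1). The values of g are assumptions.

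| g | rectal | intravesical | vaginal | transdermal |
|---|---|---|---|---|
| 0.98 | 0.98 | 0.96 | 0.94 | 0.92 |
| 1.05 | 1.05 | 1.10 | 1.16 | 1.22 |

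The data could neither reveal nor exclude either row.

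**5. Carryover is not the problem.** Seven days is 168 h. For assumed half-lives of 0.5 to 5 h that is 168/0.5 = 336 down to 168/5 ≈ 34 half-lives.

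**6. A balanced order.** A five-treatment Williams design has 10 sequences, one per planned subject. Each route falls in each period twice, and each of the 20 ordered neighbour pairs occurs twice.
- Rank with route 18, without 14: all 4 route df are free, and residual df are 50 − 18 = 32.
- Variance of a route-minus-intravenous contrast: 0.20σ² with 10 completers. With any 8 of the 10 sequences, all 4 df remain and the variance is 0.25σ² to 0.2625σ².
- Raw route means are less robust. Of the 45 ways to lose two sequences, only 5 keep every route at the same mean period. In the worst case two routes differ by 0.875 of a period (for example 3.5 − 2.625), which leaves 0.875d. A period term removes it.

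**7. Randomising only the middle three routes.** Intravenous is still always first and transdermal always last, so their raw contrast keeps the full 4d. Ranks with 10 subjects: 16 − 14 = 2 of 4 route df.

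**The case against.** The strongest defence is that this is a descriptive, unpowered pharmacokinetic study. Its primary outcome is plasma concentration over time; within-route concentrations, Cmax, tmax and half-lives need no contrast between routes. No between-route comparison of sleepiness, reaction time or symptoms is specified. This stands, and it limits the point to bioavailability and to the side-by-side reading that five parallel summaries invite.

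Three stronger readings are tempting, and the documents do not support them.
- *Practice distorts bioavailability.* Learning a reaction-time test cannot change plasma AUC. A session-1 denominator biases f only if clearance or the assay drifts with session number, and nothing in the documents indicates that either does.
- *No analysis can undo the problem.* Every session has its own baseline for sleepiness and reaction time, so change from baseline removes an additive session shift without any change of order. The plan does not specify it, and it would not remove learning within a session.
- *Intravenous will look slower by 20–40 ms.* The drift is assumed. In raw scores, practice would make the first session look slow. In change from baseline, learning within session 1 could make it look fast and mask sedation. The direction depends on the summary used.

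The remedy also has a real logistic cost, set out under the fix.

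**Conclusion.** The point holds in this limited form. Route is completely aliased with session number for every analysed subject, and neither the washout nor the menstruation rule changes that. Reaction time is the clearest exposure, because prior practice is a fixed function of route and the plan has neither a practice run nor a baseline-adjusted summary. Sleepiness and symptom reports are plausibly open to habituation. Bioavailability is exposed only to period effects other than practice, of unknown and possibly small size. The primary within-route pharmacokinetic description is not undermined.

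The aliasing result needs no assumption beyond the stated order. The sizes in ms and in f rest on assumed linear or constant-ratio drifts and are illustrations, not estimates. The change is worth making because it is cheap before the first session and the order cannot be repaired afterwards.

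**What to change.** 1. Allocate the 10 subjects at random to the 10 sequences of a five-treatment Williams design, and include period in any between-route summary, since 8 completers may leave the sequences unbalanced.
2. Give each subject an unrecorded practice run of the reaction-time test before session 1.
3. Summarise sleepiness and reaction time as change from that session's own baseline over the 0–8 h window common to all five routes.

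If the fixed order has to stay for logistics, adopt items 2 and 3, state the reason for the order, and report between-route differences as confounded with session order. Randomising only the middle three routes does not free the intravenous-versus-transdermal contrast.

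Cost: protocol wording and a 10-line allocation list, with no extra sessions, samples or subjects. All formulations must be available throughout, and scheduling is less uniform. The rectal and intravesical solutions have stability data for 45 days at 25°C (Handling of melatonin formulations, Storage). One subject's sessions span at least 4 × 7 = 28 days, or 35 with a one-week postponement, so staggered entry may need repeat batches. The documents do not say that stability motivated the order.

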The melatonin will be administered rectally in a fluid, followed by plasma samples over the following 24 hours. The melatonin formulation applied for rectal administration will be a 2.5 ml fluid containing 25 mg of melatonin. The delivery of the fluid is to be performed via an enema. The subjects will be asked to defecate, if possible in the morning, prior to the administration of melatonin.

Study session 3: Intravesical administration

The melatonin/dimethyl sulfoxide (DMSO) aqueous solution will be administered intravesically, followed by plasma samples over the following 24 hours. The melatonin used in the study will be applied intravesically through a catheter at a dose of 25 mg in 50 ml of a solution of 50% (w/w) DMSO in water, the solution containing melatonin at a concentration of 0.5 mg/ml. The subjects will be asked not to consume fluids three hours prior to the start of the study day, and will be asked to void their bladder prior to administration of melatonin.

Study session 4: Vaginal administration

The vaginal suppository containing melatonin will be administered vaginally, followed by plasma samples over the following 24 hours. The melatonin used in the study will be applied at a dose of 25 mg in a suppository (Witepsol S58) vaginally, by the participant themselves.

Study session 5: Transdermal administration

The melatonin will be administered topically as 1 g of a 2.5% (w/w) melatonin cream over a skin area of 20 x 20 cm (400 cm²), followed by plasma samples over the following 48 hours. The dose of melatonin used in the study will thus be 25 mg. The participants will be asked to refrain from using any other creams or lotions one day prior to the study session, and for the following 48 hours.

Outcomes

The outcomes are identical for four of study sessions of the trial (intravenous, rectal, intravesical, and vaginal). The transdermal study session will have a follow-up of 48 hours rather than 24 hours. These differences are outlined below.

Primary outcome

Plasma concentration of melatonin at baseline, 0 min, 10 min, 20 min, 30 min, 40 min, 50 min, 1 hour, 2 hours, 3 hours, 4 hours, 6 hours, 8 hours, and 24 hours. Blood samples are drawn from a peripheral venous catheter within the first 8 hours, and the 24-hour samples will be taken as a single venipuncture. Each blood sample will have a volume of 6 ml, totaling 84 ml for each of the four first study sessions. For the blood samples drawn from a peripheral venous catheter, 4 ml of blood

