
will be drawn as “waste”, to ensure that the following 6 ml consist of undiluted blood, totaling another 52 ml of blood. In total, the subjects will have 136 ml of blood samples each study session.

For the transdermal study session, blood samples are drawn at baseline, 0 min, 30 min, 1 hour, 2 hours, 4 hours, 6 hours, 8 hours, 10 hours, 12 hours, 16 hours, 24 hours and 48 hours. Intervals are based on data from previous pharmacokinetic studies of transdermal melatonin [23]. Blood samples are drawn from a peripheral venous catheter within the first 16 hours, and the 24- and 48-hour samples will be sampled through a single venipuncture each. Each plasma sample will have a total volume of 6 ml, totaling 78 ml for the transdermal study session. For the blood samples drawn from a peripheral venous catheter, 4 ml of blood will be drawn as “waste”, to ensure that the following 6 ml consist of undiluted blood, totaling another 44 mL of blood. In total, the subjects will have 122 ml of blood drawn samples for the transdermal study session.

Plasma samples will be kept in a locked freezer (with a temperature-alarm) at the Department of Surgery, Herlev Hospital. The plasma concentration will be assessed by radioimmunoassay (RIA)-technique at Gastrolab, Herlev Hospital. RIA-technique is a validated method of determining melatonin in plasma that has been used for years [28]. A bio-bank will be created, containing solely the plasma samples from this study (see Data Management for further details). In the case report forms (CRF), the collection time of each sample will be noted. The plasma concentrations will be delivered to the investigator digitally from the laboratory, and will afterwards be noted in the through double entry CRF, by independently two investigators.

Secondary outcomes

Sedative effects and other adverse effects

A Karolinska sleepiness scale (KSS)-score will be performed at baseline and once every hour for 8 hours, as well as at 24 hours, and noted in the CRF. For the transdermal study session, the score will

be performed at every hour on the first day until 16 hours, as well as at 24 and 48 hours. The KSS is frequently used to evaluate subjective sleepiness. The scale has been validated against performance and EEG-variables [29].

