The subjects will be questioned about adverse events during each study session and at the 24-hour plasma sample (as well as at 48 hours for the transdermal study session). We have defined five pre-specified self-reported symptoms (fatigue, confusion, depressed mood, or headache), based on the most commonly reported adverse reactions of melatonin available in the literature [See attached Investigators Brochure]. Volunteers will also be asked to report additional symptoms of adverse effect, if any. Both adverse reactions and adverse events will be reported in the CRF. An adverse reaction is defined as harm or unwanted reaction to a drug, no matter the dosage. An adverse event is defined as any medical event in a patient or healthy volunteer in a clinical trial after treatment with a drug, without any necessary connection between the treatment and the undesirable event.

Serious adverse events (SAE) are defined as any medical event that result in death, are life-threatening, lead to hospitalization, result in disability or permanent damage, or any other important medical event. All serious adverse events will be registered and reported to the Danish

Medicines Agency (Lægemiddelstyrelsen) and the Danish Committee on Health Research Ethics (Videnskabetisk Komité) in a final report.

Serious adverse drug reactions (SARs) will be reported annually (most likely irrelevant to this study, as it will not continue for a full year).

Suspected unexpected serious adverse reactions (SUSARs) will be reported immediately to the Danish Medicines Agency and the Danish Committee on Health Research Ethics.

Summary of Product Characteristics and Investigators Brochure (both are attached to this document) will be used to evaluate SUSARs. Adverse event registration will commence on the first study day and be finalized after the last study day. In case of serious adverse reactions the sponsor will decide if the study is to be terminated.

Setting

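### In sessions 1–4 no sleepiness or reaction-time test is scheduled before 1 hour, so early sedation after the 10-minute intravenous infusion, or after any route peaking before 1 hour, may be missed or understated by an unknown amount

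*Combined protocol and SAP*

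**What the plan says.** Under Secondary outcomes, sedation is measured by the Karolinska sleepiness scale (KSS) and a simple reaction-time test. For sessions 1–4 the KSS rule is: "A Karolinska sleepiness scale (KSS)-score will be performed at baseline and once every hour for 8 hours, as well as at 24 hours". The reaction-time test is done at baseline and then "once every hour for 8 hours after administration of melatonin, as well as 24 hours after administration of melatonin". In the transdermal session KSS is to "be performed at every hour on the first day until 16 hours, as well as at 24 and 48 hours". The first post-dose reading is thus at 1 hour in all five sessions.

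Plasma sampling in sessions 1–4 is much denser early on: "Plasma concentration of melatonin at baseline, 0 min, 10 min, 20 min, 30 min, 40 min, 50 min, 1 hour", then 2, 3, 4, 6, 8 and 24 hours. For session 1, "The infusion of melatonin will be performed over 10 minutes".

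Outside KSS and reaction time, the Adverse events section says: "The subjects will be questioned about adverse events during each study session and at the 24-hour plasma sample". It gives no clock times within the session. Its list of pre-specified symptoms includes fatigue; the list under Secondary outcomes does not. No reason is given for starting the sedation tests at 1 hour.

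**The concern.** The stated objective covers adverse reactions by each route as well as pharmacokinetics, and sedative effects head the secondary outcomes. The plan samples plasma closely in the first hour, when the intravenous level must peak and begin to fall, but schedules no sedation test in that hour. If the 1-hour readings after intravenous dosing show little change, the data cannot tell whether there was no early sedation or whether it was not measured. The same applies to a rectal, intravesical or vaginal dose that peaks before 1 hour. Later work on local administration would then rest on an incomplete picture of sedation by route.

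**Working it through.** The plan states no figure on this point to reproduce. The check compares the time grids and then asks how much could be lost.

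**1. Grids, sessions 1–4.** Post-dose plasma: 0, 10, 20, 30, 40, 50 min and 1, 2, 3, 4, 6, 8, 24 h = 13 samples. Post-dose KSS and reaction time: 1 to 8 h hourly and 24 h = 9 readings. Six plasma samples (0–50 min) have no paired test; the other seven all have one. The count agrees with the protocol's blood volume: (13 + 1 baseline) × 6 ml = 84 ml.

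**2. Intravenous plasma at the first test.** Infusion time (10 min) is from the protocol. The half-life *h* is not given, so 20–120 min is an assumption. In a one-compartment model the peak is at the end of infusion, and the fraction left *t* minutes later is 2^(−t/h). The protocol starts a clock after dosing for the other four routes but defines no time zero for the intravenous session. The first test is therefore at t = 50 min (clock from infusion start) or t = 60 min (clock from infusion end).

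| Assumed half-life (min) | t = 50 min | t = 60 min |
|---|---|---|
| 20 | 18% | 13% |
| 30 | 31% | 25% |
| 45 | 46% | 40% |
| 60 | 56% | 50% |
| 90 | 68% | 63% |
| 120 | 75% | 71% |

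**3. From plasma to effect.** Sedation may lag plasma. With an effect compartment, dCe/dt = ke0 × (C − Ce) and ke0 = ln 2 / (equilibration half-life), solved numerically for plasma half-lives of 30, 45 and 60 min with the clock from infusion start. Effect-site level at 1 hour as a share of its maximum:

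| Assumed equilibration half-life (min) | Range over plasma half-lives |
|---|---|
| 2 | 38–63% |
| 5 | 49–73% |
| 10 | 68–87% |
| 20 | 89–99% |
| 30 | 97–100% |

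At 60 min the effect peaks about 65 to 92 min after the start, which is inside the hourly grid.

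**4. Other routes.** With first-order absorption, tmax = ln(ka/k)/(ka − k). Assumed absorption half-lives of 5–20 min and elimination half-lives of 30–60 min give tmax of about 16–48 min, and plasma at 1 hour of 43–97% of peak. Slower absorption puts the peak near or after 1 hour.

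**5. A slow route's peak against intravenous plasma at 1 hour.** In the same model, Cmax = F × (D/V) × 2^(−tmax/h), where F is bioavailability as a fraction, D the dose and V the volume of distribution. A route peaking at or after 1 hour can reach at most 2^(−60/h) of D/V, which is 0.25, 0.40 and 0.50 for h = 30, 45 and 60 min at full bioavailability. The intravenous end-of-infusion level is (1 − 2^(−10/h)) / (ln 2 × 10/h) = 0.893, 0.927 and 0.944 of D/V. Multiplying by the fractions in step 2, the level at the first test is 0.28, 0.43 and 0.53 (clock from start) or 0.22, 0.37 and 0.47 (clock from end).

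**The case against.** The strongest objection is that steps 2 and 4 concern plasma, not sedation. If the effect lags, a 1-hour reading may lose almost nothing: with an equilibration half-life of 20 to 30 minutes it catches 89% or more of the maximum. This stands. A reader might infer that the sedative effect is likely understated, but the documents give neither half-life nor lag and do not support more than a possibility.

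A reader might also infer that early sedation is never assessed. That goes too far. Subjects are questioned about adverse events during each session, may describe additional symptoms, and return after dosing to a room with the research assistant, where sedative effects are evaluated. But this questioning is untimed, fatigue is in only one of the two symptom lists, and neither list names drowsiness. It is a weak backstop and does not replace a graded score or a measured reaction time.

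The background section also reports intravenous doses of up to 100 mg in adults without adverse reactions, so early sedation may be slight. That is possible, but other cited studies did see drowsiness, and the protocol itself chose to measure sedation.

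Finally, these are secondary outcomes in a study of eight to ten volunteers with no power calculation, and an hourly grid is a legitimate design choice. That limits the weight of the point. It does not explain why the first hour is left out.

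**Conclusion.** The gap is certain: no KSS or reaction-time test is scheduled between baseline and 1 hour, and six of 13 post-dose plasma samples in sessions 1–4 have no paired reading. Its consequence is a possible loss of unknown size. For peak sedation the direction is fixed, because the highest true value on a grid without the first hour cannot exceed the true maximum. The size depends on assumptions: intravenous plasma at the first test is 13–75% of peak for half-lives of 20–120 min, and the loss of effect runs from large (little lag) to negligible (equilibration half-life of 20–30 min or more).

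A reader might go further and expect fast routes to look less sedating than slow ones. Step 5 does not support that. Intravenous plasma at 1 hour is above the highest possible slow-route peak, or at most about 11% below it (0.223 against 0.25), and it is above it in every case if the slow route's bioavailability is under about 89%. Differences between routes could be compressed, but a reversal is not shown. The Statistics section also plans no between-route comparison of sedation.

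This is a worthwhile, low-cost improvement to a secondary outcome. The primary outcome and the sample size are not affected.

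**What to change.** In sessions 1–4, add KSS at about 10 and 30 minutes, tied to the blood draws already scheduled then. Add the reaction-time test at the same times where it fits between draws. For the intravenous session, define time zero as the start or the end of infusion and take the first reading as soon as the infusion ends. Keep the hourly grid.

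Report change from baseline at each time point. Restrict any between-route summary to time points common to the sessions compared; across all five sessions these are 1 to 8 hours and 24 hours. Do not summarise by the maximum over all readings: it tends to rise with the number of readings, which would be 9 + 2 = 11 in sessions 1–4 against 16 + 2 = 18 in the transdermal session. If early readings are not added, state that sedation before 1 hour is not measured by KSS or reaction time.

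The cost is two more short tests per session and extra CRF lines, with no extra blood or visits. Timing will be tighter around the 10-minute draws, each with its waste draw, and around the move between rooms after dosing. KSS should take priority if both tests cannot be fitted in.
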